8.1.2 Collection and Reporting Serious Adverse Events

Following the subject's written consent to participate in the study, all SAEs, whether related or not related to study drug, must be collected, including those thought to be associated with protocol-specific procedures. All SAEs must be collected that occur during the screening period and throughout the course of the study up to and including the End of Treatment Visit / 30 days after last dose. The Investigator should report any SAE occurring after this time period that is believed to be related to study drug or protocol-specific procedures.

All SAEs should be followed to resolution or stabilization.

An SAE report should be completed for any event where doubt exists regarding its status of seriousness.

If the Investigator believes that an SAE is not related to the study drug, but is potentially related to the conditions of the study (such as a withdrawal of previous therapy or a complication related to study procedure), the relationship should be specified in the narrative section of the SAE Report Form.

SAEs, whether related or not related to study drug, overdose (see Section 8.3), potential drug induced liver injury (see Section 8.5) and pregnancies (see Section 8.4) must be reported within 24 hours of the Investigator becoming aware of the event. The Investigator is responsible for submitting all applicable events to the Independent Review Board (IRB) as per the IRB's reporting requirements. Additionally, the Investigator, or designated staff, is responsible for entering the SAE information into the Case Report Form (CRF) and/or system (i.e., event term, start/stop dates, causality, and severity).

Any serious adverse event must be reported immediately or no later than 24 hours after awareness of the event to PPD Pharmacovigilance (PVG). A written description of any serious adverse event, using the PPD SAE report form, must be sent to PPD PVG by facsimile (fax), which is the preferred method of submission, within 24 hours after awareness of the event:

! North America - [name]

If a form is unable to be submitted within 24 hours, the SAE may be reported by telephone via the Safety Hotline Number:

! North America – [name]

If only limited information is initially available, follow-up reports are required. If an ongoing SAE changes in its intensity or relationship to study drug or if new information becomes available, a follow-up SAE report should be sent within 24 hours of the Investigator becoming aware of the updated information using the same procedure used for the transmission of the initial SAE and the same event term should be used.

The minimum information required for an initial SAE report is:

- ! Sender of report (Site number, Investigator name)
- ! Subject identification (subject number)
- ! Protocol number
- ! SAE term (if an SAE is being reported)

8.2 Non-serious Adverse Events

A **non-serious adverse event** is an AE not classified as serious.

8.2.1 Collection and Reporting of Non-Serious Adverse Events

The collection of non-serious AE information should begin at the initiation of study drug through the Follow up Safety Visit (End of Treatment Visit).

Non-serious adverse events should be followed until conclusion or stabilization, or reported as SAEs if they become serious. Follow-up is also required for non-serious AEs that cause interruption or discontinuation of study drug or those that are present at the end of study treatment.

8.2.2 Laboratory Test Abnormalities

The following laboratory test abnormalities should be captured on the non-serious AE CRF page or SAE Report Form (paper or electronic) as appropriate:

- ! Any laboratory test result that is clinically significant or meets the definition of an SAE.
- ! Any laboratory abnormality that required the subject to have the study drug discontinued or interrupted.
- ! Any laboratory abnormality that required the subject to receive specific corrective therapy.

8.3 Overdose

An overdose is defined as the accidental or intentional administration of any dose of a product that is considered both **excessive** and **medically important**.

All occurrences of medically significant overdose (suspected or confirmed and irrespective of whether it involved BHV-3000) must be communicated to Biohaven or a specified designee within 24 hours and be fully documented as an SAE. Details of any signs or symptoms and their management should be recorded including details of any treatments administered.

Asymptomatic dosing errors (e.g., accidentally taking two tablets instead of prescribed dose of one tablet in one calendar day) should be reported as deviations.

8.4 Pregnancy

If, following the Baseline Visit, it is subsequently discovered that a study subject is pregnant or may have been pregnant at the time of the investigational product exposure, including during at least 6 half-lives after the product administration, the investigational product will be permanently discontinued in an appropriate manner (i.e., dose tapering if necessary for subject safety). Protocol-required procedures for study discontinuation and follow-up must be performed on the subject unless contraindicated by the pregnancy (i.e., x-ray studies). Other appropriate pregnancy follow-up procedures should be considered if indicated.

Sites should instruct subjects to contact the Investigator if they become pregnant during the course of the study. The Investigator must immediately notify the Biohaven (or designee) Medical Monitor and PPD of the event and complete the Pregnancy Form in accordance with SAE reporting procedures as described in Section 8.1.2. The pregnancy should be reported

using paper forms, which should be faxed to PPD PVG by facsimile (fax), which is the preferred method of submission, within 24 hours after Investigator/site awareness of the event:

! North America - [name]

Or if the form cannot be faxed or emailed ([contact]; subject line must include “Biohaven Protocol BHV3000-314”), reported via phone to the PPD Safety Hotline at North America: [name].

Once the paper form is available, the data must be reported per standard procedures.

Follow-up information regarding the course of the pregnancy, including perinatal and neonatal outcome, and where applicable offspring information must also be reported on a Pregnancy Report Form.

Any pregnancy that occurs in a female partner of a male study participant should be reported to the Sponsor/PPD. Information on this pregnancy will be collected on the Pregnancy Report Form, as appropriate.

8.5 Potential Drug Induced Liver Injury (DILI)

Wherever possible, timely confirmation of the initial liver-related laboratory abnormalities should occur prior to the reporting of a potential DILI event. All occurrences of potential DILIs, meeting the defined criteria, must be reported as SAEs as per Section 8.1.2.

Potential drug induced liver injury is defined as:

1. ALT or AST elevation > 3 times the upper limit of normal (ULN).

AND

2. Total bilirubin > 2 times ULN, without initial findings of cholestasis (elevated serum alkaline phosphatase).

AND

3. No other immediately apparent possible causes of ALT or AST elevation and hyperbilirubinemia, including but not limited to, viral hepatitis, pre-existing chronic or acute liver disease, or the administration of other drug(s) known to be hepatotoxic.

If any potential DILI is identified and meets the criteria above, the Biohaven Medical Monitor (or designee) should immediately be contacted for further instruction and whether the subject must discontinue from the trial and appropriate follow up requirements.

8.6 Adverse Events of Special Interest

None

9 STATISTICS

Complete details on the statistical methods for this study may be found in the Statistical Analysis Plan (SAP).

9.1 General Procedures

Categorical variables are tabulated with counts and percentages. Continuous variables are summarized with univariate statistics (e.g., n, mean, standard error, median, minimum and maximum).

For the calculation of descriptive statistics of observed data, subjects must have a baseline value to be evaluable for endpoints based on values and changes from baseline over time.

Tabulations of the following endpoints present the number of unique subjects with an event: protocol deviations; interruptions of study therapy; non-study medications; adverse events; and laboratory abnormalities. Thus, for these endpoints, multiple occurrences of the same event are counted only once per subject.

9.2 Sample Size

If 80% of the 200 randomized (100 per treatment arm) treat with study drug, we expect roughly 160 total or 80 per treatment group in the randomized and treated population for analysis.

Assuming rimegepant provides a 2-point reduction in NRS pain, and a 1.5-point advantage over placebo on the primary endpoint, and a common standard deviation of 3.0, then the study will have roughly 88% power on the primary endpoint.

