Version 3.0 – Amendment 2	
Synopsis and Section 2.1 Primary Objective(s): The primary objective was changed from To evaluate the efficacy of rimegepant compared with placebo in the acute treatment of Temporomandibular Disorders on change from baseline of pain on NRS (0-10) score at 2 hours post-dose. To To evaluate the efficacy of rimegepant compared with placebo in the acute treatment of Temporomandibular Disorders on the time-weighted sum of pain intensity difference from baseline scores for the first 2 hours post-dose (SPID-2).
 
Synopsis and Section 2.2 Secondary Objective(s): The secondary objectives were changed from:
 
1. To evaluate rimegepant compared to placebo on $\geq 30\%$ reduction from baseline of pain NRS (0-10) score at 2 hours post-dose. (this objective was deleted)2. To evaluate rimegepant compared to placebo on $\geq 50\%$ reduction from baseline of pain NRS (0-10) score at 2 hours post-dose. (this objective was deleted)3. To evaluate rimegepant compared to placebo on the proportion of subjects that are pain free at 2 hours post-dose.4. To evaluate rimegepant compared to placebo on the probability of requiring rescue medication within 24 hours of initial treatment. 
To
 
1. To evaluate rimegepant compared with placebo on the time-weighted sum of pain intensity difference from baseline scores for the first 24 hours post-dose (SPID-24). (this objective was added)2. To evaluate rimegepant compared to placebo on change from baseline of pain on NRS (0-10) score at 2 hours post-dose. (this was the old primary objective. It was moved and is now a secondary objective)3. To evaluate rimegepant compared to placebo on the proportion of subjects that are pain free at 2 hours post-dose.4. To evaluate rimegepant compared to placebo on time to onset of meaningful pain relief post-dose. (this is a new secondary objective)5. To evaluate rimegepant compared to placebo on time to onset of initial pain relief post-dose. (this is a new secondary objective)	31 March 2022
---------------------------	---	---------------

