	
associated with mechanically induced arthralgia
 
(2) Hypomobility disorders other than disc disorders (I.2.B)
 
(3) Hypermobility disorders (I.2.C.)
 
New text:
 
i. Joint Disorders:
 
(1) Disc disorders (I.2.A.1-4) only when associated with mechanically induced arthralgia
 
(2) Other hypomobility disorders (I.2.B), such as adhesions/adherence, ankylosis
 
(3) Hypermobility disorders (I.2.C.), such as subluxation, luxation
 
In addition, Contracture (II.2) was added as vii, which also caused the remainder of the list under section 2.C to be renumbered viii through xi.
 
Section 5.3, 1.d was clarified as follows:
 
From:
 
d. Subject has a history of neuropathic/idiopathic pain disorder.
 
To:
 
d. Subject has a history of neuropathic (e.g., trigeminal neuralgia, postherpetic neuralgia) or idiopathic pain disorder.
 
Section 5.3 Exclusion Criteria, 5.g.: Severe hepatic impairment (Child-Pugh C) is exclusionary in all cases was added.
 
Section 9.2 Sample Size was updated from If 80% of the 200 randomized (100 per treatment arm) have a TMD associated pain reaching intensity of ≥ 6 on the NRS prior to treatment, and provide at least one post baseline efficacy data point, we expect roughly 160 total or 80 per treatment group in the Modified Intent to Treat (mITT) population for analysis. To If 80% of the 200 randomized (100 per treatment arm) treat with study drug, we expect roughly 160 total or 80 per treatment group in the randomized and treated population for analysis.
	
--	--	--

--	--

The third paragraph in Section 9.3 Population for Analysis was updated from The set of treated subjects consists of all subjects who take study therapy (rimegepant or placebo) to The set of treated subjects consists of all **randomized** subjects who take study therapy (rimegepant or placebo).

In addition the following paragraph was deleted from Section 9.3: *The mITT set consists of randomized subjects that take study therapy, have a TMD associated pain in the jaw and/or temple area which reaches pain intensity of ≥ 6 on the NRS (0-10) prior to treatment, and provide at least one post baseline efficacy data point.*

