9.4.2 Primary Endpoint(s)

The SPID-2 will be calculated by multiplying the PID score (difference between NRS at each time point and baseline NRS) at each post-dose timepoint by the duration (in hours) since the preceding timepoint, then summing the values over the 2 hours. This is analyzed on the treated population using an analysis of covariance (ANCOVA) model that includes the baseline NRS (0-10) value as a covariate, and main effects for treatment group and stratification factor (use of daily medications / oral devices to reduce the intensity of TMD symptoms).

The least squares mean (LS mean), standard error (SE), and 95% confidence interval (CI) for each treatment group will be reported, as well as the difference estimate (rimegepant - placebo), SE, 95% CI, and p-value.

Intercurrent events will be treated as failures, with the assumption that the subject does not improve once the intercurrent event occurs. In the event a subject uses a non-study rescue medication on or before 2 hours post-dose, all data points after rescue medication was administered will be set to the last available observation prior to rescue medication usage (RM = Rescue medication use: F = Failure). Likewise, if a subject fails to log their pain score at any time after study drug is administered, through 2 hours post-dose, this data will be imputed to the last available observation (NC = Non-completers; F = Failure).

Sensitivity analyses will be described in the SAP.

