9.4.3.2 Change from Baseline of Pain on NRS

The change from baseline of pain on NRS score at 2 hours post-dose will be analyzed with a generalized linear mixed effect model that includes subject as a random effect, the baseline NRS (0-10) value as a covariate, and fixed effects for treatment group, stratification factor (use of daily medications / oral devices to reduce the intensity of TMD symptoms), scheduled time point, and time point by treatment group interaction. Time points included in the model are nominally at 15, 30, 45, 60, 90 and 120 minutes post-dose. Repeated measurements within-subject will be modeled using an unstructured covariance structure for within-subject error. In the case that the model fails to converge, a Huynh-Feldt error structure will be attempted, followed by an AR(1) structure. Error degrees of freedom will be calculated using a Kenward-Roger approximation. The difference estimate (rimegepant - placebo), SE, 95% CI, and p-value will be reported for 2 hours post-dose.

Intercurrent events of use of a non-study rescue medication at or before 2 hours post-dose, or if a subject fails to log their pain score at any time after study drug is administered through 2 hours post-dose, will be handled in the same manner as they are for the primary endpoint.

9.4.3.3 *Pain Freedom at 2 Hours*

The number of subjects that are pain free at 2 hours post-dose will be analyzed after first imputing missing data at 2 hours to be failure (NC = F). Additionally, subjects who use rescue medication on or before assessment of pain at 2 hours will also be assigned as failures (RM = F). The analysis will be done using a stratified Cochran-Mantel-Haenszel (CMH) test after imputation is done, with the stratification factor as use of daily medications / oral devices to reduce the intensity of TMD symptoms.

9.4.3.4 *Time to Onset of Meaningful Pain Relief*

Time to onset of meaningful pain relief post-dose will be defined as the first nominal timepoint at which a 30% reduction of pain from baseline on NRS is achieved. This will be analyzed using Kaplan-Meier methods for a “time to event” analysis. Rimegepant will be compared to placebo using a log-rank test which will compare the survival distributions. Intercurrent events will be handled in the same manner as they are for the primary endpoint.

9.4.3.5 *Time to Onset of Initial Pain Relief*

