Time to onset of initial pain relief post-dose will be defined as the first nominal timepoint at which a 1-point reduction of pain from baseline on NRS is achieved. This will be analyzed using Kaplan-Meier methods for a “time to event” analysis. Rimegepant will be compared to placebo using a log-rank test which will compare the survival distributions. Intercurrent events will be handled in the same manner as they are for the primary endpoint.

9.4.3.6 *Rescue Medication Use through 24 Hours*

The number of subjects that use rescue medication through 24 hours post-dose will be analyzed using a stratified CMH test, with the stratification factor as use of daily medications/oral devices to reduce the intensity of TMD symptoms.

9.4.4 *Adjustment for Multiplicity*

Type 1 error is addressed in this study using a gatekeeping procedure. The significance of the primary endpoint is evaluated at the two-sided alpha level of 0.05. If the primary endpoint is significant, then the secondary endpoints are tested using Hochberg’s procedure.

CCI

9.4.5 *Missing Data*

For the primary and secondary endpoints of SPID-2, SPID-24, change in NRS from baseline, time to onset of meaningful pain relief, and time to onset of initial pain relief, subjects who fail to record their pain during the timeframe of interest for each endpoint will be considered

failures (NC = F) and this data will be imputed to the last available observation prior to the missing data occurrence.

For the secondary endpoint of proportion of subjects that are pain free at 2 hours post-dose, missing data at 2 hours post-dose will be imputed as a failure (NC = F), and these subjects will not be considered as having achieved pain freedom.

For the secondary endpoint of proportion of subjects who use rescue medication through 24 hours-post dose, there will be no imputation for missing data, the analysis will be based on non-missing, observed data.

Additional methods for handling of missing data, including sensitivity analyses, will be described in detail in the SAP.

9.4.6 *Rescue Medication*

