5 SAMPLE SIZE, POWER, AND TYPE I ERROR

If 80% of the 200 randomized (100 per treatment arm) treat with study drug, we expect roughly 160 total or 80 per treatment group in the randomized and treated population for analysis.

Assuming rimegepant provides a 2-point reduction in NRS pain, and a 1.5-point advantage over placebo on the primary endpoint, and a common standard deviation of 3.0, then the study will have roughly 88% power on the primary endpoint.

Type 1 error is not applicable. The significance of the primary and secondary endpoints will not be evaluated.

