The pain intensity difference at each post-baseline timepoint (PID_i) is calculated by finding the difference between the NRS score at each timepoint (PI_i) from the baseline NRS score (PI_0).

$$PID_i = PI_i - PI_0$$

The SPID-2 will be calculated by multiplying the PID score at each post-dose timepoint by the duration (in hours) since the preceding timepoint, then summing the values over the 2 hours.

$$SPID - 2 = \sum_{i=1}^6 (T_i - T_{(i-1)}) * PID_i$$

Where $T_0 = 0$, T_i = the nominal time as described in Table 3, $T_{(i-1)}$ = the preceding nominal time, PID_i = PID score at time T_i

Table 3: NRS Collection Nominal Timepoints

NRS collection timepoint	i	T_i (hours)
15 minutes	1	0.25
30 minutes	2	0.50
45 minutes	3	0.75
60 minutes	4	1.00
90 minutes	5	1.50
2 hours	6	2.00
4 hours	7	4.00
8 hours	8	8.00
24 hours	9	24.00

The SPID-2 will be analyzed on the treated population using an analysis of covariance (ANCOVA) model, estimated by Restricted Maximum Likelihood (REML) that includes baseline NRS value as a covariate and treatment group and stratification factor (use of daily medications / oral devices to reduce the intensity of TMD symptoms) as the main effects. The least squares mean (LS mean), standard error (SE), and 95% confidence intervals (CI) for each treatment group will be estimated and reported, as well as the LS mean, SE, and 95% CI for the difference between treatment groups (rimegepant – placebo). Descriptive summaries of PID value at each measured timepoint will be presented by treatment group to include mean, SD, median, minimum, and maximum.

The intercurrent events of non-study rescue medication and failure to log NRS pain score are treated with a composite strategy. All assessments after rescue medication administration are set to the last observation prior to the time of rescue medication use. Any missing NRS assessment(s) will be imputed to the last non-missing observation prior to the missing assessment. For clarity, in the case of intermittent missing values, missing values will be imputed based on the last non-missing observation prior to the missing value or consecutive series of missing values; any subsequent non-missing values will not be imputed unless rescue medication was administered prior to that assessment. Subjects who mistakenly dose and thus have a missing baseline NRS assessment will have the missing baseline assessment imputed as the mean of the non-missing baseline assessments across subjects.

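### Does the 88% power in Protocol 9.2 and SAP 5 apply to SPID-2, when the unit of the 1.5 and the 3.0 is not stated?

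*Protocol*

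**What the plan says.** Protocol 9.2 and SAP 5 carry the same sample-size text. Of 200 randomized subjects, 80% are expected to treat, leaving about 80 per arm. The assumptions are "a 2-point reduction in NRS pain, and a 1.5-point advantage over placebo on the primary endpoint, and a common standard deviation of 3.0", and the result is stated as "then the study will have roughly 88% power on the primary endpoint".

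The primary endpoint is SPID-2. Protocol 9.4.2 takes the pain intensity difference (PID) "at each post-dose timepoint by the duration (in hours) since the preceding timepoint, then summing the values over the 2 hours". SAP 6.3.2.1 agrees: "The SPID-2 will be calculated by multiplying the PID score at each post-dose timepoint by the duration (in hours) since the preceding timepoint". Its Table 3 gives nominal times of 0.25, 0.5, 0.75, 1, 1.5 and 2 hours. SPID-2 is therefore measured in NRS points times hours (NRS-hours).

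The NRS change at 2 hours is a separate, secondary endpoint with its own model. Protocol 9.4.3.2 says: "The change from baseline of pain on NRS score at 2 hours post-dose will be analyzed with a generalized linear mixed effect model".

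On testing, Protocol 9.4.4 says: "The significance of the primary endpoint is evaluated at the two-sided alpha level of 0.05". SAP 1 records that the study ended early, in 1Q2023, for low enrollment. SAP 5 then states that Type I error does not apply and that significance will not be assessed for the primary or secondary endpoints.

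**The concern.** One sentence seems to mix two scales. The 2-point reduction is expressly in NRS pain, the 1.5 is a number of points on the primary endpoint, and the 3.0 has no unit. An SD of 3.0 could be an SD of SPID-2 or an SD of a single score on a 0-10 scale. Neither document converts NRS points to NRS-hours or cites a source for the SD.

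Two things would be at stake. The first is the planned effect: 1.5 NRS-hours over 2 hours is an average advantage of 0.75 points, half of what a reader might take from a 1.5-point advantage. The second is the power itself. If 1.5 and 3.0 describe the NRS score at 2 hours, power for SPID-2 depends on the time course of the effect and on within-subject correlations, and the documents give neither.

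**Working it through.** **Inputs.** n = 80 per arm, difference 1.5 and SD 3.0 (Protocol 9.2, SAP 5); two-sided alpha 0.05 (Protocol 9.4.4); SPID-2 weights from SAP Table 3 of 0.25 h four times and 0.5 h twice, which sum to 2 h.

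**Step 1: reproduce the stated figure.** The noncentrality is difference / (SD × √(2/n)) = 1.5 / (3.0 × √(2/80)) = 1.5 / 0.4743 = 3.162. The normal approximation gives Φ(3.162 − 1.960) = 88.5%. The noncentral t with 158 degrees of freedom gives 88.2%. Both match the stated 88%. Other inputs do not: one-sided 0.05 gives 93.5%, 100 per arm gives 94.2%, and a difference of 2.0 gives 98.8% (normal approximation). The 2-point reduction therefore plays no part in the power.

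**Step 2: both inputs in NRS-hours.** This is the plain sense of an advantage on the primary endpoint. The calculation is that of step 1, so power for SPID-2 is 88.2%. The average advantage is 1.5 / 2 h = 0.75 points.

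**Step 3: both inputs as PID averaged over the 2 hours.** Multiplying by 2 h gives a SPID-2 difference of 3.0 and an SD of 6.0. The ratio is still 0.5 and power is still 88.2%. The planned effect is an average of 1.5 points.

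**Step 4: both inputs as NRS change at 2 hours.** A time course, an SD profile and a correlation must now be assumed. With an advantage of 1.5 points at 2 h, the SPID-2 difference is Σ(weight × advantage):

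- no effect through 60 min, full at 90 and 120 min: 0.5 × 1.5 + 0.5 × 1.5 = 1.50
- linear rise to 2 h: 0.75 × (0.25 × 2.5 + 0.5 × 3.5) = 1.78
- linear rise to full at 1 h, then flat: 1.5 × (0.25 × 2.5 + 0.5 × 2) = 2.44
- constant from 15 min: 1.5 × 2 = 3.00

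The SPID-2 SD is √(w′Σw), where w holds the weights and Σ is the covariance matrix of the six scores. For SD 3.0 at every time and equal correlation ρ, the variance is 9 × [0.75(1 − ρ) + 4ρ]. That gives an SD of 4.62 at ρ = 0.5 and 5.75 at ρ = 0.9. If the SD grows with the square root of time to 3.0 at 2 h, the SPID-2 SD is 3.48 to 4.26. If it grows linearly with time, it is 2.87 to 3.44. Power (noncentral t, 80 per arm), from ρ = 0.5 to ρ = 0.9:

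| Effect course | SD 3.0 throughout | SD grows as √time | SD grows linearly |
|---|---|---|---|
| None through 60 min | 53% to 37% | 77% to 60% | 91% to 78% |
| Linear to 2 h | 68% to 50% | 90% to 75% | 97% to 90% |
| Full by 1 h | 91% to 76% | 99% to 95% | above 99% |
| Constant | 98% to 91% | above 99% | above 99% |

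The results fall on both sides of 88%. Every time course, correlation and SD profile in this step is an assumption from outside the documents, and no gain from the baseline covariate is counted. The table shows that the power cannot be derived on this reading; it does not show that 88% is too high.

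**Step 5: which reading fits the text.** The sentence attaches both the 1.5 and the power to the primary endpoint, which is SPID-2. Step 2 needs nothing beyond those words. Step 3 needs SPID-2 to be expressed as an average, although both documents define it as a sum. Step 4 needs the primary endpoint to mean what Protocol 9.4.3.2 lists as secondary.

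**The case for a change.** The best argument for a change comes from the protocol's history. The Amendment 2 summary says of the 2-hour NRS change: "this was the old primary objective. It was moved and is now a secondary objective". The entry that begins "Section 9.2 Sample Size was updated from If 80% of the 200 randomized (100 per treatment arm" replaces one description of the analysis population with another and lists no new difference or SD. The 1.5 and 3.0 may thus have been chosen for the 2-hour score and carried over. On that account the stated power has no basis for SPID-2, and one line of text would settle it. SAP v2.0 also repeats the 88% although the test it refers to has been dropped.

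Part of this stands. The unit is not stated, and a reader cannot tell from the text alone whether the planned average advantage was 0.75 or 1.5 points. A mixed reading, 1.5 in NRS-hours with an SD of 3.0 in NRS points at every time, would also give lower power: 54% to 35% for correlations of 0.5 to 1.0 (normal approximation). It requires two scales for a difference and an SD given side by side.

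The rest does not carry. An amendment summary describes superseded text, and unchanged inputs do not show that they are on the wrong scale. The low powers in step 4 depend on a late effect combined with an SD already at 3.0 at 15 minutes; with an SD growing linearly, the same late effect gives 78% to 91%. Calling the 88% power for the 2-hour change would leave the primary endpoint with no power statement. As for the SAP, its sentence is conditional on 200 being randomized, the next paragraph says significance will not be evaluated, and SAP 1 reports the early stop.

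**Conclusion.** No change is needed. The stated power is reproduced at 88.2%, and it holds for SPID-2 on the plain reading of the sentence and also on the time-averaged reading. It would lack support only if the inputs were taken off the SPID-2 scale, as with the 2-hour NRS change. That reading fits the wording worst, and its effect on power cannot be calculated from the documents in either direction.

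What remains is an unlabelled unit in a planning statement. A statistician who reads 1.5 and 3.0 as the SPID-2 difference and SD obtains the stated result at once. The number of subjects actually treated was settled by early termination. SAP v2.0 reports SPID-2 least squares means, standard errors and 95% confidence intervals without a p-value, and none of these uses the 1.5, the 3.0 or the 88%. Adding the unit would tidy the record but would alter no estimate, interval or conclusion. This rests on taking the phrase about the primary endpoint at face value, on 80 per arm and on a two-sided 0.05 test.
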